9.1. Parameters to be monitored

Participants will complete a nicotine patch toleration test during the orientation visit. Nursing staff will apply the dose-matched nicotine patch at the end of the nurse assessment and will describe potential side effects to the participant. Participants will wear the patch for approximately 3 hours and will be asked to notify the LI or nursing staff immediately if they experience any worrisome side-effects.

Participants will be instructed during their orientation visit, and on the phone immediately prior to the commencement of each abstinence period, on the potential side effects of nicotine administration via transdermal patch. The details of what side effects are possible, when to remove the patch, and details of who to contact should participants experience side effects are clearly outlined in the Nicotine Patch Instructions (Appendix 5) which participants will take home with them from the orientation session. During telephone and in-person assessments participants will be directly asked open-ended questions will be used to assess for the presence of adverse effects. During placebo-patch and nicotine scans heart rates will be monitored via pulse oximeter. After completion of the scan, nursing will remove the patch and measure blood pressure and heart rate.

Based on Pfizer and FDA's ongoing safety review of post-marketing reports, Pfizer have modified the varenicline label in the U.S. to include a warning that patients who are attempting to quit smoking with varenicline should be observed for serious neuropsychiatric symptoms, including changes in behavior, agitation, depressed mood, suicidal ideation, and suicidal behavior. However, a recent cohort study based on the UK General Practice

Principal Investigator: [name].

Research Database (N = 80, 660) found no significant difference between varenicline and nicotine replacement therapy in reported incidents of fatal and non-fatal self-harm (0.16% vs 0.22%), suicidal ideation (0.05% vs 0.05%) or initiation of anti-depressant use (3.18% vs 3.62%) (Gunnell, Irvine, Wise, Davies, & Martin, 2009). Nevertheless, to help mitigate potential risks related to changes in mood, behavior, or suicidal ideation and to assess for all side effects, a clinical monitoring plan involving weekly in-person assessments during the 12-week treatment period will be implemented. During their initial treatment interview (the day they set their quit date) or during their final pretreatment visit they will briefly meet with the study MAI or the designated NIDA-IRP physician in the MAI's absence who will distribute a 2 weeks supply of varenicline and carefully describe the medication, prescribed dosing schedule and possible side-effects. Participants will also receive a set of take-home instructions and information sheet (see Appendix 8). During each weekly visit across the entire 12-week treatment participants will receive a nurse assessment to assess vital signs and complete a series of questionnaires (see Appendix 4). During their counseling session the therapist will administer a semi-structured interview (see Appendix 7) to assess for psychiatric and physical symptoms. If participants are unable to attend their weekly counseling session in person, study therapists, LI or study clinician will conduct telephone assessments to monitor for changes in physical and psychiatric symptoms (administering the varenicline toleration assessment, Appendix 7). The same assessment will also be conducted each week for the first two weeks after their last Varenicline dose. At any time during the study, endorsement of one or more items listed in Appendix 7 will be referred to the study MAI or a NIDA-IRP clinician in the MAIs absence to who will determine if the endorsement requires further action. Participants with suicidal ideations, atypical changes in behavior, or experiencing clinically significant or difficult to tolerate side effects may be provided with a referral, instructed to stop taking the study pills, and/or be withdrawn from the study.

Date: March 2, 2022

Study therapists will be extensively trained and supervised in administration of the semi-structured interview by the study MAI. The participant will be referred to the MAI if any questions or issues arise.

At each visit to NIDA, participants are queried about their general medical and emotional health (including current medications and drug use history) since their last visit to NIDA and are observed throughout each visit at NIDA by study investigators. Any change in health status is noted by protocol staff and evaluated for relevance to the participant's participation. Investigators will refer the participant to the MAI for any medical adverse events or questions about recent medical conditions. The MAI will be informed of and respond to any adverse events.

- (1) All female participants will have a urine pregnancy test performed before each visit that requires an MRI.
- (2) All participants participating in an MRI study will receive a comprehensive screening for metal and other possible devices within the body that are contraindicated in the MRI environment.
- (3) The MRI is for research purposes only and not the type used to look for neurophathological changes; they will not be routinely reviewed for such problems. However, sometimes the MRI will show what could be an abnormal finding. In this case, the participant will be referred to the proper expert(s) for further diagnostic procedures.

Medical Emergencies. During fMRI sessions, which will take place at NIDA-IRP arrangements are in place for the emergency transport of subjects to the Johns Hopkins Bayview Emergency Department, if required.

Principal Investigator: [name].

9.2. Criteria to be used

Participants who experience a serious expected or unexpected adverse event (i.e., require hospitalization, experience significant disability/incapacitation, death, or have a life-threatening reaction) with likely or greater relationship to the experimental procedures will be excluded from any further participation. Participants may also be withdrawn from the study should they experience a serious allergic reaction to the nicotine or placebo patch adhesive. Should participants fail to comply with the 36 hr smoking abstinence, they will be asked to reschedule their scanning visit and recomplete the 36 hr abstinence. If they do not wish to reschedule, they will be withdrawn from the study.

Date: March 2, 2022

No specific data on the toxic dose of varenicline appear to be available. The toxic dose of varenicline may be dependent on previous experience with nicotine. Specifically, smokers are able to tolerate higher single-doses of varenicline than non-smokers (Faessel et al., 2006a). Varenicline is well tolerated in single doses up to 3mg (Faessel et al., 2006a) and in multiple doses up to and including 2mg daily (Faessel et al., 2006b) with nausea and vomiting being limiting factors. Participants may be discontinued from varenicline treatment and offered alternative treatment (i.e., nicotine replacement therapy) depending on the severity of varenicline related side effects. The daily dose of varenicline may be reduced (on a case-by-case basis) to alleviate side effects and increase retention rates if necessary.

9.3. Criteria for individual subject withdrawal

Individual participation will be terminated if the individual no longer wishes to participate, is continually non-compliant (repeatedly fails to show for appointments without calling to reschedule, does not complete procedures as instructed, does not comply with restrictions such as limited caffeine use, drug use), if they no longer meet study inclusion criteria, or if a circumstance arises that makes continued participation unsafe or ill-advised (for example, an inability to tolerate nicotine patch; participants will be allowed to continue in the study without varenicline if they cannot tolerate it). Subjects will also be withdrawn if they do not complete the following required procedures:

- 1) the two pre-treatment scan visits;
- 2) set a quit date;
- 3) attempted to quit for at least 24 hours;
- 4) we have been able to establish their quit status (i.e., relapsed vs non-relapse) at 1, 6 OR 12 months following their last treatment visit.

Principal Investigator: [name].

10. Outcome measures

10.1. Primary outcomes measures

1) Change in BOLD signal and FC related to task parameters, between drug conditions: will provide important insight into the neurobiological mechanisms underlying acute nicotine withdrawal, in particular those related to anhedonia, negative affect, inhibitory control and impulsive decision making.

Date: March 2, 2022

- 2) Behavioral performance on each of the tasks assessing inhibitory control processes, reward responsiveness, amygdala, striatal, BNST reactivity and impulsive decision making (e.g., reaction time, error rate, hit rate, reward bias): will provide task-related parameters necessary for analysis of BOLD data. Performance data will function as a secondary outcome by providing behavioral validation of acute nicotine withdrawal effects.
- 3) Self-reported craving, withdrawal symptoms and mood/affect: will be employed as regressors in the analysis of task and resting BOLD data. They will also provide the primary means of validating the acute nicotine withdrawal manipulation.
- 4) Smoking status at 1, 6 and 12 months: Smoking status (relapse vs abstinent) at each of the follow-up time points will be based on 7-day point prevalence defined as no smoking (not even a puff) or use of any tobacco products for the past 7 days. This is a standard method of assessing abstinence and dichotomizing relapse status at follow-up (Keating & Siddiqui, 2006; Leventhal et al., 2008; Swan et al., 2010b). Whenever abstinence at follow-up is assessed in-person, self-reported abstinence will be corroborated with breath CO and urine cotinine levels.

10.2. Secondary outcome measures include:

- 4) MRS for glutamate concentration: Glutamate concentration at the PFC and hippocampus is expected to change as a function of acute nicotine withdrawal and may also play a role in the expected reduction in VS reactivity and anhedonia.
- 5) Plasma ACTH and cortisol: are expected to increase as a function of acute nicotine withdrawal and is expected to play role in both anhedonia and negative affective symptoms, potentially by acting at the amygdala, BNST and VS.
- 6) Resting state CBF from ASL: To test for changes in neural activity (i.e., not connectivity) at rest it is necessary to employ a measure which does not require a baseline. CBF provides such a measure as changes in blood flow are referenced to a common arterial location outside of the brain.
- 7) ERP and EEG measures: Secondly, ERP and EEG indices will provide information about neural processing that cannot be derived from the BOLD signal and will be important to dissociating temporally tightly coupled processes underlying inhibitory control.

Principal Investigator: [name].

8) Ratings and scores on self-report characterization measures: will be employed to examine potential mediation of primary hypothesized effects. E.g., does degree of nicotine dependence mediate craving related changes in rsFC in the DMN?

Date: March 2, 2022

9) Structural MRI and DTI data: will be employed to examine potential mediation of primary hypothesized effects. E.g., does increased WM integrity between the rACC and amygdala effect rsFC between these two structures and in turn amygdala reactivity?

Resting state MRI at follow-up. Resting state MRI will be assessed between- and within-groups as a function of relapse status and time since last treatment visit at each of the three follow-up time-points (1, 6 and 12 months). This will allow us to address the following exploratory questions:

- Q1. What characteristics of rsFC are associated with treatment success (vs failure) at 1, 6 and 12 months post-treatment?
- Q2. Are there characteristics of rsFC that vary as a function of time post-treatment in successfully abstinent individuals?

11. Statistical Analysis

11.1. Pre-processing

The imaging data will be pre-processed with AFNI (Analysis of Functional NeuroImages, http://afni.nimh.nih.gov/afni/ (Cox, 1996)) and Brainvoyager 1.7 (BrainInnovation, Masstricht, The Netherlands). All functional images will be directly registered upon high resolution MPRAGE anatomical scans obtained during the same imaging session. Location and intensity of activations from individual and/or grouped data will be translated into 3D stereotaxic coordinates (Talairach and Tournoux, 1988). Functional images of activation-induced BOLD signal changes will be determined using cross correlation or multiple regression analyses (Worsley and Friston, 1995; Bandettini and Wong, 1997).

Glutamate concentrations derived from MRS will be quantified for the PFC/ACC and or hippocampus with LCModel software. The LCModel software utilizes a library of reference spectra and a curve fitting algorithm to estimate the tissue concentration of neural metabolites. Values are given in institutional units approximating millimolar (ppm) concentration.

EEG/ERP data will be pre-processed and analyzed using commercially (BrainVision Analyzer) and freely available (Delorme and Makeig, 2004) software packages. Individual and group ERPs will be calculated and the amplitude of selected components (e.g., ERN, P300, evoked theta). BESA (Brain Electrical Source Analysis, MEGIS, Germany) will also be used to identify the putative neural generators of ERP components using dipole source models.

11.2. Data-Analysis

Unless otherwise specified, all BOLD, genetic, behavioral, self-report and physiological data will be analyzed with AFNI or R (http://www.R-project.org; R Development Core Team, 2008). The types of statistical analysis to be utilized in the current protocol are summarized below.

Nicotine deprived vs non-deprived. Between condition (nicotine-deprived vs non-deprived) comparisons will be conducted on self-report, behavioral, BOLD ROI, resting CBF and ERP responses with a series of one-way repeated measures ANCOVAs, with nicotine-deprivation (nicotine-deprived vs non-deprived) as the within-subjects factor and nicotine dose as the covariate. By controlling for nicotine dose we can partially dissociate the

Principal Investigator: [name].

effects from acute nicotine-withdrawal effects. Treatment seeking status (Treatment seeking vs non-treatment seeking) will be included as a between-subjects factor in these models to assess the main effects and of motivation to quit as well as any interaction between motivation to quit and acute nicotine withdrawal.

Date: March 2, 2022

Mediation. Where mediation has been hypothesized (e.g., central CRF as a mediator of VS reactivity following acute nicotine withdrawal), regression coefficients for the paths of each mediation model will be derived with multiple regression and the mediation effect will be tested with ProdClin (Mackinnon, Fritz, Williams & Lockwood, 2007). ProdClin is a program developed by MacKinnon, Fritz, Williams, and Lockwood (2007) that uses the distribution of the product of paths a and b to compute asymmetric confidence intervals for the mediated effect. ProdClin is an alternative to the Sobel (1982) method that provides a more powerful and accurate test of the mediation effect because it is based on an asymmetric distribution which more closely resembles the true distribution of the product terms. Mediation models will be conducted separately for treatment-seeking and non-treatment seeking smokers.

Functional Connectivity. Seed regions for FC will be based on peak BOLD responses in ROIs for the parameter of interest. Strength of functional connectivity will be measured by correlating the BOLD time-series between seed and target regions. Fisher r to z transformations will be conducted to test for significant differences in functional connectivity strength between the non-deprived and nicotine-deprived conditions. Treatment seeking status (Treatment seeking vs non-treatment seeking) will be included as a between-subjects factor in these models to assess the main effects and of motivation to quit as well as any interaction between motivation to quit and acute nicotine withdrawal.

Correlational analyses. Bivariate partial correlations controlling for nicotine dose will also be conducted between self-report and behavioral indices of acute nicotine withdrawal and BOLD indices. Correlational analyses will serve to identify neural markers of responsivity to nicotine replacement. A series of bivariate partial correlations (controlling for nicotine dose) will also be conducted between BOLD, EEG, psychophysiological and neuroendocrine markers between nicotine-deprived and non-deprived conditions. Correlations will be conducted separately for non-treatment and treatment seeking groups.

Genotype by nicotine-deprivation interaction. 2 x 2 mixed-design ANOVAs will be conducted with genotype (short vs long allele of the 5-HTTLPR gene) varied between-subjects, and nicotine-deprivation (nicotine deprived vs non-deprived) varied within-subjects. The DVs will be BOLD signal change and functional connectivity. Treatment seeking status (Treatment seeking vs non-treatment seeking) will be included as a between-subjects factor in these models to assess the main effects and of motivation to quit as well as any interaction between motivation to quit and acute nicotine withdrawal.

RSN dynamics under acute nicotine withdrawal. The presence of three independent RSNs resembling the ECN, DMN and SN will be confirmed by applying an Independent Component Analysis (ICA) to the band pass filtered (0.01 to 0.08 Hz) resting BOLD time-series. ICA analysis will be conducted using the FSL Melodic ICA software (http://www.fmrib.ox.ac.uk/analysis/research/melodic/). The time-series of six seed regions reflecting core-nodes within each of these networks (ECN: dlPFC, PPC; DMN: vmPFC, PCC; SN: dACC, anterior insula) will then be regressed against each other to assess within and between network rsFC. Fisher r to z transformations will be applied to assess changes in rsFC between nicotine-deprived and non-deprived conditions. Bivariate partial correlations (controlling for nicotine dose) will also be conducted between the degree of change in rsFC within/between the three networks and changes in self-reported affective/cognitive withdrawal symptoms/urge to smoke as well as changes in working memory and attention indices. Treatment seeking status (Treatment seeking vs non-treatment seeking) will be included as a between-subjects factor in these models to assess the main effects and of motivation to quit as well as any interaction between motivation to quit and acute nicotine withdrawal. Correlations will be conducted separately for non-treatment and treatment seeking groups.

Principal Investigator: [name].

Relapse vs non-relapse group comparisons. Neurobiological processes underlying acute nicotine withdrawal will be assessed as a function of relapse status at each of the follow-up time-points by conducting between group comparisons.

Date: March 2, 2022

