2.1. Primary goals

To characterize the neurobiological mechanisms underlying acute nicotine withdrawal and the maintenance of smoking behavior in current cigarette smokers. To achieve this, the current protocol will employ multiple task-based and resting state measures to probe the anhedonic and anxiogenic effects of acute nicotine withdrawal as well as reported inhibitory control deficits and increased impulsive decision-making. Changes in RSN dynamics will also be examined in relation to affective and cognitive symptoms associated with acute nicotine withdrawal. Acute nicotine-withdrawal will be manipulated by assessing dependent smokers twice: once in a non-deprived state (following 36 hours of smoking abstinence during which time they will continually wear a dose-matched nicotine patch) and on a second occasion in a nicotine-deprived state (following 36 hours of smoking abstinence whilst wearing a placebo patch). In the nicotine-deprived condition smokers are expected to report anhedonia and negative affective symptoms and associated changes in mesolimbic dopaminergic pathways

Principal Investigator: [name].

as well as amygdala and BNST functioning. As illustrated in Figure 1, we expect these changes to drive inhibitory control deficits and elevated impulsive decision making by altering functioning within and between intrinsic default mode, executive control and salience networks. Finally, the extent to which neurobiological changes resulting from acute nicotine withdrawal predict success of treatment for smoking cessation will be assessed.

Date: March 2, 2022

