2.3. Aims and hypotheses

Aim 1: To examine the effect of acute nicotine withdrawal on self-reported anhedonia and its relationship to reward responsiveness and striatal reactivity, and in turn the extent to which these withdrawal-related neurobiological processes predict treatment success. Acute nicotine withdrawal produces a state of anhedonia and reduced reward responsiveness. Preclinical work suggests that these effects may result from reduced dopamine release at the NAcc (manifesting in reduced striatal reactivity), mediated by increased central CRF and potentially by reduced glutamate signaling in a circuit from the PFC to the NAcc, and potentially the hippocampus.

Measures: Self-reported anhedonia; behavioral and EEG indices of reward responsiveness; BOLD response and functional connectivity during striatal reactivity task; task measure of striatal reactivity, EEG and behavioral correlates of reward responsiveness.

Mediators: Plasma ACTH; Glutamate concentration at the PFC/ACC and/or hippocampus measured with MRS.

Hypothesis 1.1: Compared with nicotine satiety, acute nicotine withdrawal will result in increased self-reported anhedonia, accompanied behavioral correlates of reward responsiveness and reduced ventral striatal reactivity. The degree of reduced striatal reactivity and reward responsiveness will in turn predict treatment success.

Principal Investigator: [name].

Hypothesis 1.2: The effect of acute nicotine withdrawal on striatal reactivity will be partially mediated by an increase in plasma adrenocorticotropic hormone (ACTH; an index of central CRF).

Date: March 2, 2022

Hypothesis 1.3: Acute nicotine withdrawal will result in reduced glutamate measured with MRS at the hippocampus and PFC, with the latter predicting reduced PFC-NAcc connectivity. Reduced PFC glutamate, as well as reduced PFC-NAcc signaling will partially mediate the predicted reduction in ventral striatal reactivity.

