In the current study we aim to increase the severity of nicotine-withdrawal effects by employing a 36 hour deprivation period. At the same time, individual differences in responsivity to nicotine replacement will likely reduce between-condition effects relative to smoking deprivation vs smoke adlib studies cited above. Together the above studies suggest that the weakest effects of a dose-matched nicotine vs placebo manipulation in 36 hr deprived smokers smoking deprivation manipulation will arise for behavioral measures and will be medium in size (d = 0.5). We selected a power level (1- β) of 0.80 to achieve an appropriate balance between the ability to detect significant differences and the number of participants needed. Assuming an alpha-level of 0.05, a correlation among repeated measures of r = 0.5 and a medium effect size, approximately 35 participants will be required to achieve a power of 0.80 (calculated by G*Power http://www.psycho.uniduesseldorf.de/abteilungen/aap/gpower3/).

Motivation to quit by nicotine-deprivation. To generate an estimated effect size for a 2 (treatment seeking vs non-treatment eeking) x 2 (deprived vs non-deprived) we referred to the single study conducted to date comparing treatment seeking smokers to non-treatment seeking smokers (Wilson et al., 2012). In this study, which employed self-report physiological and neuroimaging outcome measures, the smallest effect size reported for a 2 x 2 between-within interaction, where the between subjects factor was treatment seeking status, was $\eta^2 = .08$. Based on an effect size of $\eta^2 = .08$, and a power of 0.80, and an estimated correlation between repeated measures of 0.5, the required sample size to detect a true 2 x 2 between-within interaction effect is 26 individuals.

Genotype by nicotine-deprivation. To derive an estimated effect size for the genotype by nicotine-deprivation interaction we examined effects of the 5-HTTLPR polymorphism on pharmacological manipulations where conditions are varied within-subjects. Genotype by treatment effects on behavioral and self-report outcome

Principal Investigator: [name].

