Correlational. Bivariate partial correlations (controlling for nicotine dose) will be conducted between the change in BOLD, ERP/EEG, psychophysiological and neuroendocrine markers, behavioral and self-report under nicotine-deprivation (relative to nicotine satiety). Large effects (d > 0.80) are typically observed between changes in self-report (e.g., craving, withdrawal symptoms) and BOLD measures (e.g., insula or amygdala activity or functional connectivity) during smoking abstinence relative to smoke adlib (Cole et al., 2010; Kozink et al., 2010a; McClernon et al., 2009b). Similarly large effect sizes are reported between changes in behavioral indices (e.g., RT variability) and BOLD responses (e.g., PCC task response) under nicotine (relative to placebo) in minimally deprived smokers (Hahn et al., 2007). Large effect sizes also arise between BOLD responses and neuroendocrine and psychophysiological markers (Ahs, Sollers, Furmark, Fredrikson, & Thayer, 2009; Drevets et al., 2002) as well as between behavioral indices and time-to-smoke in the laboratory relapse model (Dallery & Raiff, 2007). Based on a slope of 0.59 between each predictor and outcome measure (a large effect size according to J. Cohen, 1988) a sample size of at least 20 would be required to achieve a power of 0.80. (Calculated by G*Power, http://www.psycho.uniduesseldorf.de/abteilungen/aap/gpower3/).

Mediation Analyses. Based on the literature reviewed above, we expect a large effect size between each predictor, outcome and mediation variable in the mediation models described above. Based on a large effect size for paths *a* and *b*, Fritz and McKinnon (2007) suggest a sample of 35 to achieve a 0.80 power to detect each mediation effect with Prodclin.

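### Does Section 11.2's silence on how the two sessions enter the mediation regressions put the mediation results at risk?

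*Combined protocol and SAP*

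**What the plan says.** Section 11.2 presents its contents as a summary of the types of analysis. The mediation paragraph states that "regression coefficients for the paths of each mediation model will be derived with multiple regression and the mediation effect will be tested with ProdClin" and that the models are run separately for treatment-seeking and non-treatment-seeking smokers. It names no change score, participant term or centring.

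The cause in these models varies within person. Section 2.1 says: "Acute nicotine-withdrawal will be manipulated by assessing dependent smokers twice". Hypotheses 1.2, 1.3, 2.1, 2.2 and 3.1 route withdrawal effects through a mediator. Hypothesis 1.3, for example, reads: "Reduced PFC glutamate, as well as reduced PFC-NAcc signaling will partially mediate the predicted reduction in ventral striatal reactivity".

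Neighbouring analyses do state the pairing. The condition comparisons are repeated-measures ANCOVAs. The genotype models have "nicotine-deprivation (nicotine deprived vs non-deprived) varied within-subjects". The resting-network correlations are taken "between the degree of change in rsFC within/between the three networks and changes in self-reported affective/cognitive withdrawal symptoms/urge to smoke". In Section 11.4 the correlational paragraph concerns "the change in BOLD, ERP/EEG, psychophysiological and neuroendocrine markers, behavioral and self-report under nicotine-deprivation (relative to nicotine satiety". On mediation, Section 11.4 says only "we expect a large effect size between each predictor, outcome and mediation variable in the mediation models described above" and cites a methods paper for a sample of 35 at power 0.80.

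**The concern.** An analyst could take the mediation sentence literally, put both sessions in one file, regress the mediator on condition, and regress the outcome on condition and mediator. Path b would then absorb any stable correlation across people. Smokers with habitually high ACTH and a habitually strong amygdala response would give a non-zero b even if the withdrawal-induced rise in ACTH did nothing to the amygdala. Combined with a real rise in ACTH, the product test would report mediation. These models carry the mechanism claims of Aims 1 to 3, so a wrong unit of analysis would matter. The error can also run the other way and hide a true mediated effect.

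**Working it through.** **Inputs.** From the documents: two sessions per person; groups of 35 and 85; alpha 0.05; 0.59 as a large slope (Section 11.4, correlational); "a correlation among repeated measures of r = 0.5 and a medium effect size" (Section 11.4, condition comparisons, borrowed here); condition effect d = 0.5. Assumed: a mediator shift of 0.8 SD as a second value, and the correlation ρ between smokers' usual mediator and outcome levels. The documents do not give ρ, so a range is shown. The 85 are completers defined by quit status at follow-up, whereas mediation needs only both scans, so the treatment-seeking number could differ.

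**1. The plan's own figure.** Take one independent record per person, M = 0.59X + e, Y = 0.59M + e, with unit error variances. The ProdClin interval excludes zero when P(AB<0) = Φ(−z_a)Φ(z_b) + Φ(z_a)Φ(−z_b) is below 0.025 or above 0.975. Simulated power at N = 35 is 0.81 (continuous X) or 0.83 (balanced two-valued X). At N = 34 it is 0.79 with continuous X. The figure of 35 reproduces.

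**2. Size of the bias if sessions are stacked.** Let the true within-person b be 0, each session have SD 1, and a share r of variance be stable between people. After condition is removed, the stacked slope is b = r × ρ.
- ρ = 0.3: b = 0.5 × 0.3 = 0.15. With a 0.8 SD shift, ab = 0.12.
- ρ = 0.5: b = 0.5 × 0.5 = 0.25, and ab = 0.20.

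**3. Rough frequency by hand (ρ = 0.3).** SE(b) ≈ √(1 − 0.15²)/√(2N).
- N = 35: 0.989/√70 = 0.118; z = 1.27; P(Z > 1.96 − 1.27) ≈ 0.25.
- N = 85: 0.989/√170 = 0.0758; z = 1.98; P(Z > 1.96 − 1.98) ≈ 0.51.

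These take path a as detected. Stacked, SE(a) = √(2/35) = 0.239 at N = 35. A shift of 0.5 then gives z = 2.09 and is often missed, which lowers the product rate there.

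**4. Simulated false mediation, stacked rows, session r = 0.5.**

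| N | Mediator shift (SD) | ρ = 0 | 0.2 | 0.3 | 0.5 |
|---|---|---|---|---|---|
| 35 | 0.5 | 3% | 8% | 12% | 27% |
| 35 | 0.8 | 8% | 15% | 25% | 53% |
| 85 | 0.5 | 8% | 26% | 47% | 85% |
| 85 | 0.8 | 8% | 28% | 51% | 90% |

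Varying session r from 0.3 to 0.8 (ρ = 0.3, shift 0.8) moves the rate from 11% to 52% at 35 and from 22% to 84% at 85.

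**5. Same data, paired.** Deprived-minus-non-deprived differences, or equivalently person fixed effects, give 4.0-6.3% in every cell above.

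**6. Does the existing wording admit the paired model?** Path a is the mean mediator change, the intercept of a regression of that change on centred dose. Path b is the slope of outcome change on mediator change. Both are multiple-regression coefficients with standard errors, and ProdClin takes exactly those. Nothing in the paragraph has to be altered to run it.

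**7. Power of the paired model at 35.** With b = 0.59, it is 85-90% for mediator shifts of 0.59-1.18 SD and 74% at 0.5 SD. With an assumed medium b of 0.39, it is 48-62%. The stated 35 is not shown to be too small under the plan's premise of large paths.

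**The case for a change.** The best case for amending is that the silence is real and the stacked reading is not far-fetched. In a stacked file path a is an ordinary coefficient on condition, whereas in a change-score file condition disappears and path a becomes an intercept. A half-measure also fails: a random person intercept alone still gives 29% false mediation at 35 and 59% at 85 (ρ = 0.5, shift 0.8). The harm can also take the form of lost power: with ρ = −0.5 and a true b of 0.59, power at 35 is 10% stacked against 90% with differences. A sentence would cost nothing in data or visits.

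What stands is that the unit of analysis is unstated, and that a careless choice would be costly wherever usual levels correlate. What does not stand is the step from silence to a faulty plan. No passage describes unpaired rows, and every neighbouring analysis that states its handling pairs the sessions. Hypotheses 1.2 and 2.1 describe the mediator as a rise in ACTH, which is a change. Section 11.4 names changes in the very classes of variable (BOLD, neuroendocrine) used as mediator and outcome. The sample size of 35 gives no support to stacking either: it counts people with one record each, as a change-score file does, not 70 session rows.

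Nor is fixing one form throughout a clear gain. Hypothesis 1.3 has glutamate predicting connectivity as well as both acting on the striatum. Entering both changes in a single outcome model, with no regression of connectivity change on glutamate change, would lose that chain. Under a purely serial path with a shift of −0.5 and slopes of 0.59, the glutamate-specific effect is about 0.00, although −0.5 × 0.59 × 0.59 = −0.17 is carried through.

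**Conclusion.** No change to the plan is called for. This is a missing detail in a section that summarises methods, and the plan's own pattern points to the sound choice. Under that choice false mediation stays at 4.0-6.3%.

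The adverse figures (12-25% at 35 and 47-51% at 85 for ρ = 0.3) need two things the documents do not contain: a decision to stack sessions without isolating within-person variation, and a non-zero correlation between smokers' usual mediator and outcome levels. At ρ = 0 the rate is 3-8%. The figures also rest on a session correlation of 0.5 borrowed from the condition comparisons and on mediator shifts of 0.5-0.8 SD. The conclusion would change only if the sponsor stated that sessions are to be stacked, or handled with a random intercept alone.
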